5.8 Analysis of Safety Data

The summary of safety and tolerance will be performed based on the safety population.

The safety analysis will be based on the reported AEs, clinical laboratory evaluations, vital signs, physical examination, 12-lead ECG, and immunogenicity.

The potentially clinically significant abnormality (PCSA) values are defined as abnormal values considered medically important by the sponsor according to predefined criteria/thresholds ([Appendix 10.3](#)) based on literature review and defined by the sponsor for clinical laboratory tests, and vital signs.

Treatment-emergent PCSA is any PCSA developed or worsened in severity compared to the baseline during the treatment-emergent period. The time interval to detect any event or abnormality is between the first injection of study drug and EOS. All evaluations performed during the time interval will be taken into account when determine which patients had at least one PCSA, including unscheduled or repeated evaluations.

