11.4.4 Analyses of safety data

The summary of safety results will be presented by treatment group. All safety analyses (includes reported TEAEs and other safety information as clinical laboratory evaluations, vital signs, and 12-lead ECG results) will be performed on the safety population using the following common rules:

- The baseline value is defined generally as the last available value before randomization.

For safety variables, two observation periods are defined:

- The pre-treatment period is defined as the time from signing the informed consent form (ICF) to before the first dose of IMP.
- The TEAE period is defined as the time from first dose of IMP (Day 1) to the end of the study.

The following definitions will be applied to clinical laboratory evaluations, vital signs and ECG.

- The potentially clinically significant abnormality (PCSA) values are defined as abnormal values considered medically important by the sponsor according to predefined criteria/thresholds based on literature review and defined by the sponsor for clinical laboratory tests, vital signs, and ECG.
- PCSA criteria will determine which patients had at least 1 PCSA during the on-treatment period, taking into account all evaluations performed during the on-treatment period, including unscheduled or repeated evaluations. The number of all such patients will be the numerator for the on-treatment PCSA percentage.

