11.4.4.1 Adverse Events

All Adverse events reported in this study will be coded using Medical Dictionary for Regulatory Activities (MedDRA®) in effect at the time of database lock. The analyses of adverse events will focus on TEAEs.

Definitions

Pretreatment AEs are defined as AEs that developed or worsened during the pre-treatment period.

Treatment-emergent adverse events are defined as AEs that developed or worsened during the treatment-emergent period. The treatment-emergent period is from first administration of IMP to end of the follow-up period.

Treatment-emergent adverse events (TEAE)

The incidence tables will present by system organ class (SOC) (sorted by internationally agreed order), high-level group term (HLGT), high level term (HLT) and preferred term (PT) sorted in alphabetical order for each treatment group, the number (n) and percentage (%) of patients experiencing an TEAE. Multiple occurrences of the same event in the same patient will be counted only once in the tables within a treatment phase. The denominator for computation of percentages is the safety population within each treatment group.

TEAEs will also be summarized by severity and relationship to IMP for each treatment group, presented by SOC and PT.

Death

The following deaths summaries will be generated:

- Number (%) of patients who died by study period (TEAE, on-study) and reasons for death summarized on the safety population by treatment received.
- Death in nonrandomized patients or randomized and not treated patients
- TEAE leading to death (death as an outcome on the AE CRF page as reported by the Investigator) by primary SOC, HLT, HLT and PT showing number (%) of patients sorted by internationally agreed order of SOC and alphabetic order of HLT, HLT, and PT.

Listings will be provided for all deaths by treatment group and patient with flags indicating on-treatment status.

Serious adverse events:

Number (%) of patients with at least one treatment emergent SAE will be summarized by treatment group and presented by primary SOC (sorted by internationally agreed order), HLT, HLT, and PT sorted in alphabetical order. SAEs will also be listed by treatment group and patient.

TEAEs leading to permanent treatment discontinuation:

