1.3 Modifications from the Statistical Section in the Final Protocol

Modifications from the Amended protocol 1 (final protocol)

1. concomitant medication/procedure

Any concomitant treatment is considered from the first dose of study drug in the SAP instead of the time of informed consent in the protocol.

2. Potentially clinically significant abnormality (PCSA)

PCSA is applied to clinical laboratory evaluations and vital signs in SAP, while PCSA was applied to ECG as well in the protocol.

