3.3 Safety Population

The safety population consists all randomized patients who receive any IMP. Patients will be analyzed according to the treatment they actually received (as treated).

The actual treatment group is defined by the following rules:

- For patients on placebo but accidentally exposed to dupilumab, the treatment group allocation for as-treated analysis will be dupilumab
- For patients on dupilumab but accidentally received placebo, the actual treatment group allocation for as-treated analysis will be the treatment as randomized if at least one dose or part of a dose of dupilumab was received
- For patients on dupilumab but accidentally received placebo, the actual treatment group allocation for as-treated analysis will be placebo if the patient did not exposed to any dupilumab

In addition:

- Nonrandomized but treated patients will not be part of the safety population, but their safety data will be presented separately
- Randomized patients for whom it is unclear whether they took the IMP will be included in the safety population as randomized

Treatment compliance/administration and all clinical safety variables will be analyzed using the safety population.

The pre-treatment period is defined as the time from signing the informed consent form (ICF) to before the first dose of IMP. The treatment emergent period is defined as the time from first dose of IMP (Day 1) to the end of the study.

For safety summarizes, three analysis period are defined as follows:

- On-treatment period is defined as day 1 to the day of last dose of IMP + 14 days or early termination date from study, whichever comes first
- Follow-up period is defined as the last dose of IMP + 15 days to the date of the end of study
- Overall study period is defined as day 1 to the date of the end of study, consisting of both the treatment and follow-up periods

The safety population will be the basis for the analyses for the week 16 treatment period and overall study period; however, for the analyses for the follow-up period, only a subset of safety population will be included, which is defined as the patients who entered the follow-up and had at least one visit after week 16 treatment visit.

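### Protocol 11.4.4 calls for an on-treatment PCSA percentage, but the SAP specifies only a count through Week 28 and no PCSA summary by period

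*SAP*

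**What the plan says.** The protocol has two wordings.

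- Section 11.4.4 states "PCSA criteria will determine which patients had at least 1 PCSA during the on-treatment period" and then "The number of all such patients will be the numerator for the on-treatment PCSA percentage". It does not say when the on-treatment period ends. The same section announces "For safety variables, two observation periods are defined", and these are a pre-treatment period and a TEAE period: "The TEAE period is defined as the time from first dose of IMP (Day 1) to the end of the study".
- Sections 11.4.4.2 (laboratory) and 11.4.4.3 (vital signs) ask for the number and percentage of patients with a treatment-emergent PCSA. Section 11.4.4.1 gives the length of that period: "The treatment-emergent period is from first administration of IMP to end of the follow-up period".

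The SAP takes up the second wording.

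- Section 5.8 defines treatment-emergent PCSA against baseline and fixes the interval: "The time interval to detect any event or abnormality is between the first injection of study drug and EOS".
- Section 3.3 supplies the definition that the protocol lacks: "On-treatment period is defined as day 1 to the day of last dose of IMP + 14 days", or the early termination date if that is earlier. It also defines a follow-up period and an overall period for safety summaries.
- Section 5.8.1 applies the three-way split to adverse events. Sections 5.8.2 and 5.8.3 each list one treatment-emergent PCSA summary and name no period.
- Section 1.3 declares one PCSA change from the protocol, and it concerns ECG only: "PCSA is applied to clinical laboratory evaluations and vital signs in SAP, while PCSA was applied to ECG as well in the protocol".

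**The concern.** Safety of dupilumab monotherapy against placebo is a secondary objective. The protocol names an on-treatment PCSA percentage, and no SAP section specifies one, although SAP 3.3 has the period ready. As written, a laboratory or vital-sign abnormality that first appears at Week 28 counts the same as one that appears at Week 8 during dosing. The last planned dose is at Week 14. Both documents explain the 12-week follow-up as the time expected for drug levels to fall below quantification in most patients.

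Two things are at stake. If abnormalities arise at similar rates in both arms after treatment, adding them pulls the between-arm ratio towards 1. A reader of the table also cannot tell whether an excess arose on treatment or afterwards. Both problems are larger for patients who stop IMP early, because they are asked to attend all remaining visits.

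**Working it through.** **1. Length of the added interval.** Inputs from the schedule of events: last dose Week 14 = Day 99; end of study Week 28 = Day 197. Input from SAP 3.3: on-treatment ends at last dose + 14 days.

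- End of on-treatment period: 99 + 14 = Day 113.
- Added interval: 197 − 113 = 84 days; 84 / 7 = 12.0 weeks. This reproduces the stated 12-week follow-up.
- Share of the SAP interval: 84 / 197 = 43%.

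For a patient whose last dose is at Week 4 (Day 29) and who does not resume, on-treatment ends at 29 + 14 = Day 43. The Week 8, 16 and 28 panels are then all post-treatment, and all count.

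**2. Scheduled post-baseline evaluations, patient who completes dosing** (schedule of events; SAP 4.5.2 and 4.5.3).

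| Evaluation | On treatment | After treatment | Share after |
|---|---|---|---|
| Chemistry/hematology | Weeks 8, 16 | Week 28 | 1 of 3 |
| Urinalysis | Week 16 | Week 28 | 1 of 2 |
| Weight | Week 16 | Week 28 | 1 of 2 |
| Other vital signs | Weeks 2, 4, 8, 12, 16 | Weeks 20, 24, 28 | 3 of 8 |

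**3. What pooling could do to a comparison.** The documents give no PCSA rates, so these are assumptions: independent risk at each chemistry panel, d on dupilumab and c on placebo during treatment, and c in both arms at Week 28.

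- On-treatment: 1 − (1 − d)² against 1 − (1 − c)².
- Through end of study: 1 − (1 − d)²(1 − c) against 1 − (1 − c)³.

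| d, c | On-treatment | Ratio | Difference | Through Week 28 | Ratio | Difference |
|---|---|---|---|---|---|---|
| 4%, 2% | 7.8% vs 4.0% | 1.98 | 3.9 points | 9.7% vs 5.9% | 1.65 | 3.8 points |
| 10%, 5% | 19.0% vs 9.8% | 1.95 | 9.3 points | 23.1% vs 14.3% | 1.62 | 8.8 points |
| 15%, 5% | 27.8% vs 9.8% | 2.85 | 18.0 points | 31.4% vs 14.3% | 2.20 | 17.1 points |

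The ratio falls in every row. The risk difference loses less than one point.

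**4. Can the SAP 3.3 cut be applied as it stands?** The schedule allows ±3 days on both the Week 14 dose and the Week 16 visit.

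- Shortest gap: (113 − 3) − (99 + 3) = 8 days.
- Longest gap: (113 + 3) − (99 − 3) = 20 days.

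A strict cut at last dose + 14 days would move some Week 16 panels into follow-up. Week 16 is one of only two scheduled on-treatment chemistry/hematology panels, so a visit rule is needed.

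**The case against.** The strongest answer is that the SAP does not contradict a clear protocol rule. The protocol never defines on-treatment, says that two periods exist for safety variables, and asks for treatment-emergent PCSAs in both table specifications. SAP 5.8 implements that. This stands: the conflict lies partly inside the protocol, and a reader who infers a plain SAP departure from the protocol goes too far. It does not dispose of the point, because Protocol 11.4.4 still names an on-treatment percentage that no SAP section specifies.

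Second, the SAP 5.8 sentence covers events as well as abnormalities, yet adverse events are still split by period, so it may be only an outer limit. SAP 3.3 defines its periods for safety summaries in general. By-visit changes from baseline are planned, and the laboratory listing shows PCSAs by patient and visit. It is therefore not certain that a single pooled PCSA table will be produced. What is certain is that no period is named, and listings do not give between-arm percentages.

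Third, follow-up is a time of declining drug levels, so a count through Week 28 is legitimate. This stands, and that count should be kept.

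A reader might also infer that follow-up findings are contaminated by later systemic therapy. The documents do not support that as a fact. Such drugs are prohibited throughout the study except as rescue, and no expected use is given. Systemic rescue can also occur before Week 16, so a period split would not reliably remove it.

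**Conclusion.** The point holds as a gap in specification. The SAP adopts one of two unreconciled protocol wordings, leaves the on-treatment PCSA percentage unspecified and does not declare this in 1.3. For a patient who completes dosing, the pooled interval carries 84 post-treatment days, 1 of 3 chemistry/hematology panels and 3 of 8 vital-sign visits; for early stoppers it carries more.

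The effect on results cannot be sized from the documents. The illustrations rest on assumed, independent risks that are equal in both arms after treatment. They show a diluted ratio and an almost unchanged risk difference, so the main loss is attribution. SAP Appendix 10.1 makes laboratory and vital-sign analyses descriptive, so sample size, power and type I error are untouched. The change is still worth making, because it serves a stated objective, uses periods already defined and needs no new data.

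**What to change.** - In SAP 5.8, 5.8.2 and 5.8.3, report treatment-emergent PCSA percentages separately for the on-treatment, follow-up and overall periods of SAP 3.3, as SAP 5.8.1 does for adverse events. The count from first injection to end of study becomes the overall column. Use the follow-up subset in SAP 3.3 as the follow-up denominator.
- State that the scheduled Week 16 (end of treatment) evaluation of a patient who completes dosing counts as on-treatment even if it falls more than 14 days after the last dose, and that follow-up starts after it, so that no evaluation counts in both periods.
- State whether an abnormality that persists from treatment into follow-up counts again in the follow-up column, because SAP 5.8 judges emergence against baseline.
- Reconcile Protocol 11.4.4 with 11.4.4.2 and 11.4.4.3, and record the resulting change in SAP 1.3.

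The cost is SAP wording, a period flag in the PCSA programs, extra table columns and one visit-assignment rule.

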If medically necessary (ie, to control intolerable AD symptoms), rescue treatment for AD with otherwise prohibited medications or procedure (see [Section 8.8.1](#)) may be provided to study patients at the discretion of the Investigator. Please refer to the label of the product for the usage of rescue treatment. For the purpose of efficacy analysis, patients who receive rescue treatment during the study treatment period will be considered treatment failures, but they will continue study treatment if rescue consisted of topical medications. Topical calcineurin inhibitors may be used for rescue, but should be reserved for problem areas only, eg, face, neck, intertriginous, and genital areas. If possible, Investigators should attempt to limit the first step of rescue therapy to topical medications, and escalate to systemic medications only for patients who do not respond adequately after at least 7 days of topical treatment. If a patient receives rescue treatment with systemic corticosteroids or nonsteroidal systemic immunosuppressive/immunomodulating drugs (cyclosporine, methotrexate, mycophenolate mofetil, azathioprine, Janus kinase inhibitors, biologic agents, etc), the IMP will be immediately discontinued. After the treatment with these medications is completed, the IMP may be resumed if deemed appropriate by the Investigator and the sponsor, but not sooner than 5 half-lives after the last dose of systemic rescue medication. All patients will complete the schedule of study visits and assessments whether or not they complete the treatment with the IMP and whether or not they receive rescue treatment for AD. Investigators should make every attempt to conduct efficacy and safety assessments (eg, disease severity scores, safety labs) immediately before administering any rescue treatment. An unscheduled visit may be used for this purpose if necessary.

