2.2 Sample Size and Power Considerations

A total of 160 patients (with a randomization ratio of 1:1, 80 patients in each of the dupilumab 300 mg q2w and the placebo groups) will be enrolled in this study.

[figure not shown]
The study will have 94% power to detect the difference between dupilumab and the placebo. It is based on the following assumptions:

- The percentages of patients who achieve an IGA score of 0 to 1 and a reduction from baseline ≥ 2 points at Week 16 are 37% and 12% for dupilumab and placebo, respectively.
- A two-sided continuity corrected Chi-square test with the significance level of 0.05.

Calculations were made using nQuery Advisor 7.0 Software.

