4.5.2 Laboratory Safety Variables

Hematology, chemistry, urinalysis, and serum pregnancy testing samples will be analyzed by a central laboratory. The urine pregnancy test kit will be provided to the site by the laboratory.

Blood samples for serum chemistry and hematology testing will be collected at screening (day -7 to day -35), baseline (Day 1), Week 8, Week 16 (EOT), Week 28 (EOS), ET and unscheduled visits. Total basophil and eosinophil counts are of particular interest in AD patients, due to the occurrence of basophil histamine release and eosinophilia in this population. Understanding the lymphocyte profiles of AD patients may help researchers understand disease heterogeneity. Blood samples should be collected after a 6 to 8 hour fast, if possible; fasting is not mandatory.

Blood Chemistry

Sodium	Total protein (serum)	Total bilirubin
Potassium	Creatinine	Total cholesterol
Chloride	Blood urea nitrogen	Low-density lipoprotein
Carbon dioxide	Aspartate aminotransferase (AST)	High-density lipoprotein
Calcium	alanine aminotransferase (ALT)	Triglycerides
Glucose	Alkaline phosphatase	Uric acid
Albumin	Lactate dehydrogenase	Creatine phosphokinase (CPK)

Note: Direct and indirect bilirubin will be measured when the total bilirubin is above the upper limit of normal (ULN); CPK isoenzymes will be reflexly measured when CPK >5 ULN

Hematology with Differential

Hemoglobin	WBCs differential:
Hematocrit	Neutrophils
Red blood cells (RBCs)	Lymphocytes
White blood cells (WBCs)	Monocytes
Red cell indices	Basophils
Platelet count	Eosinophils

Urinalysis

Urine samples for urinalysis will be collected to measure overall patient health at screening (day -7 to day -35), baseline (Day 1), Week 16, Week 28 (EOS), ET and unscheduled visits.

Color	Glucose	RBC
Clarity	Blood	Hyaline and other casts
pH	Bilirubin	Bacteria
Specific gravity	Leukocyte esterase	Epithelial cells
Ketones	Nitrite	Crystals
Protein	WBC	Yeast

Note: Microscopic analysis will only be done in the event of abnormal dipstick results

Pregnancy testing (serum or urine) will be performed for all women of childbearing potential at screening (day -7 to day -35), baseline (Day 1), Week 4, Week 8, Week 12, Week 16 (EOT), Week 28 (EOS), ET and unscheduled visits.

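### The treatment-emergent PCSA table counts unscheduled tests, and pre-rescue safety labs are requested, so laboratory testing can depend on rescue use; add a scheduled-visit table beside it

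*SAP*

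**What the plan says.** Protocol 8.2.2 states: "Investigators should make every attempt to conduct efficacy and safety assessments (eg, disease severity scores, safety labs) immediately before administering any rescue treatment". It allows an unscheduled visit for the purpose, and SAP 4.3 repeats the instruction.

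SAP 4.5.2 places blood chemistry and hematology at screening, then "baseline (Day 1), Week 8, Week 16 (EOT), Week 28 (EOS), ET and unscheduled visits". That leaves three scheduled post-baseline draws: Weeks 8, 16 and 28. Urinalysis has two, at Weeks 16 and 28.

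For treatment-emergent PCSA, SAP 5.8 looks from first injection to end of study, and all evaluations in that interval are "taken into account when determine which patients had at least one PCSA, including unscheduled or repeated evaluations". SAP 6.4 confirms that unscheduled measurements count toward PCSA. Protocol 11.4.4 also takes in all evaluations, "including unscheduled or repeated evaluations", but limits them to the on-treatment period.

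The firmly planned PCSA summary is the number and percentage of patients by arm (SAP 5.8.2 for laboratory, 5.8.3 for vital signs); shift tables are optional. No scheduled-visit version is planned, and no count of tests per patient.

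Protocol 11.4.8 sends extra laboratory and vital-sign assessments from non-protocol visits to listings and keeps them out of summaries. SAP 1.3 records one PCSA change from the protocol, the removal of ECG. It mentions neither the window nor the treatment of extra assessments.

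**The concern.** A count of patients with at least one abnormal value rises with the number of times each patient is tested. If rescue triggers additional tests and the arms differ in rescue, the percentages can differ with no drug effect on any laboratory value.

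Rescue is a treatment-affected outcome: the primary analysis itself scores a rescued patient as a non-responder. It is given to control intolerable symptoms, so more rescue on placebo is the natural expectation. In that case the placebo percentage is raised and an increase on dupilumab looks smaller beside it. Eosinophils, which SAP 4.5.2 singles out as of interest and which have a PCSA threshold in SAP 10.3, are among the parameters exposed. With only the planned table, a reader cannot tell how much of a difference reflects testing frequency.

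**Working it through.** **The plan's own figure.** SAP 2.2 gives the only design calculation that can be reproduced. It assumes response rates that "are 37% and 12% for dupilumab and placebo, respectively", with "80 patients in each of the dupilumab 300 mg q2w and the placebo groups" and "A two-sided continuity corrected Chi-square test with the significance level of 0.05". With d = 0.25, the continuity-corrected effective size is n' = (80 − 1/0.25)²/80 = 72.2 per arm, and power is 94.5%, in line with the stated 94%. The point does not depend on this, but the two rates are the only information on how far the arms might differ in rescue.

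**Inputs for the PCSA check.**
- Scheduled post-baseline draws: 3 (SAP 4.5.2).
- Rescue share r by arm, PCSA risk per draw q, and extra draws per rescued patient: not in the documents, so assumed.
- Also assumed: no drug effect, independent draws, one extra draw per rescued patient, and no higher risk at a flare.

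**Formula.** P(at least one PCSA) = 1 − (1−q)³ × [(1−r) + r(1−q)]. The difference between arms reduces to (r_placebo − r_dupilumab) × q × (1−q)³.

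**Rescue splits.** The assumed response rates imply 88% and 63% non-response. If the same share of non-responders is rescued in each arm, 50% on placebo goes with 50% × 63/88 = 36% on dupilumab. Wider splits are shown beside it.

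| Risk per draw | Rescue, placebo / dupilumab | PCSA, placebo vs dupilumab | Excess (points) | Patients per 80 | Ratio |
|---|---|---|---|---|---|
| 2% | 50 / 36 | 6.8% vs 6.6% | 0.3 | 0.2 | 1.04 |
| 2% | 60 / 20 | 7.0% vs 6.3% | 0.8 | 0.6 | 1.12 |
| 5% | 50 / 36 | 16.4% vs 15.8% | 0.6 | 0.5 | 1.04 |
| 5% | 30 / 10 | 15.5% vs 14.7% | 0.9 | 0.7 | 1.06 |
| 5% | 50 / 20 | 16.4% vs 15.1% | 1.3 | 1.0 | 1.09 |
| 5% | 60 / 20 | 16.8% vs 15.1% | 1.7 | 1.4 | 1.11 |
| 10% | 50 / 36 | 30.7% vs 29.7% | 1.0 | 0.8 | 1.03 |
| 10% | 60 / 20 | 31.5% vs 28.6% | 2.9 | 2.3 | 1.10 |

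The ratio is therefore about 1.04 to 1.12, and the excess roughly 0.5 to 2 patients per 80 (0.2 and 2.3 at the corners). Even rescuing every non-responder (88% vs 63%) at 5% risk gives 18.0% vs 17.0%, ratio 1.06.

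**Urinalysis**, with two scheduled tests, at 5% risk and 50/20 rescue: 12.0% vs 10.7%, ratio 1.13, about one patient per 80.

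**Vital signs** have eight scheduled post-baseline visits (Weeks 2, 4, 8, 12, 16, 20, 24, 28). One extra reading adds 1/8 = 12.5%, against 1/3 = 33% for blood tests.

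**Scheduled draws only.** Both arms then have the same expectation under no drug effect: 1 − 0.95³ = 14.3% at 5% risk.

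**How easily it reverses.** At 50/20 rescue, mean draws are 3.5 on placebo and 3.2 on dupilumab. If an additional 30% of placebo patients each miss one scheduled draw, the means equalise at 3.2 and both arms sit at about 15.1%.

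**The case against.** The case against acting has real weight.

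- **Pre-rescue labs are best effort.** Safety labs are given as an example, and the schedule's footnote says not every procedure is required at an unscheduled visit. A rescue that falls at Week 8 or 16 adds no draw. This stands: the table above, with one extra draw for every rescued patient, is generous.
- **The direction is not established.** A reader might infer that placebo will be tested more and that the comparison is biased in dupilumab's favour. The documents give no rescue rate by arm. Protocol 10.1.6 also allows unscheduled tests after abnormal results or for adverse events, which could fall on either arm. The window runs to end of study and so includes off-drug weeks in which dupilumab patients may flare. Withdrawal removes scheduled draws.
- **The effect is small and the table descriptive.** At 5% risk and 50/20 rescue, the 1.3-point excess compares with a standard error of about 5.8 points for the difference. No test or decision is attached. A ratio as high as 1.54 can be produced, but only by combining 60/20 rescue, two extra draws per rescued patient and triple risk at each of them; no document supports that combination.
- **Masking is limited.** SAP 5.8.2 also plans change from baseline at each visit, and SAP 6.4 takes the scheduled value first. A sustained eosinophil rise on dupilumab would appear there, largely free of rescue-triggered tests.
- **Counting every value is sound for signal detection.** This stands, and it is why the all-evaluations table should not be replaced.

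These points limit the size and certainty of the effect. They do not remove the dependence of testing on rescue, and because the net direction is unknown, the single planned table cannot show it.

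**Conclusion.** The point holds as a modest one. The pre-rescue lab instruction and the all-evaluations rule together let the number of laboratory looks depend on a treatment-affected outcome, and no planned PCSA table separates this out. If placebo is rescued more, its percentages can be inflated by a ratio of about 1.04 to 1.12. That rests on assumed rescue shares and per-draw risks, independent draws, one extra draw per rescued patient and no flare effect. Positive correlation within a patient would shrink it; repeated draws or draws timed to flares could enlarge it.

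The documents do not support saying that the comparison is biased, that the bias favours dupilumab, or that a laboratory signal would be hidden. They support saying that it can be distorted, in a direction that cannot be known in advance. This is a cheap improvement to safety reporting and does not touch the efficacy conclusions.

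Separately, and without any assumed rates, the protocol and SAP disagree on whether extra assessments enter summaries and on the PCSA window.

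**What to change.** - **SAP 5.8 and 5.8.2:** keep the all-evaluations PCSA table for signal detection, labelled as including rescue-triggered and other unscheduled tests.
- **Add** the same laboratory table restricted to scheduled visits: hematology and chemistry at Weeks 8, 16 and 28; urinalysis at Weeks 16 and 28.
- **Report** the number of laboratory evaluations per patient by arm, so that any difference in testing is visible.
- **SAP 5.8.3:** a matching vital-sign table is optional.
- **Reconcile** Protocol 11.4.8 (extra assessments in listings only) and the Protocol 11.4.4 on-treatment window with SAP 5.8 (all evaluations, to end of study), and record the resolution in SAP 1.3.

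The cost is some SAP wording, one further run of an existing table on a flagged subset and a simple count, all best specified before unblinding. Trial conduct does not change. The scheduled-visit table will miss abnormalities found only at unscheduled tests; these stay in the all-evaluations table and the listings.
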